11.1.1.2. Random Coefficient Regression Model (RCRM)

Table 2 lists key variables that will also be analyzed in RCRM. This model will include treatment, baseline value and treatment-by-time interaction as fixed effects. Both intercept and continuous time in days are included as random effects. Unstructured covariance structures will be used for slope and intercept. If convergence is not achieved, then compound symmetry covariance structure (type=cs) is used and/or the random intercept may be removed. Restricted maximum likelihood and Kenward Rogers (1997) method for degrees-of-freedom will be used.

This same analysis will be performed with and without multiple imputation as described in Section 7.3.3.5. Each individual/combined active arm will be compared with combined placebo arm.

aTyr Pharma, Inc.
 Study ATYR1923-C-002 Statistical Analysis Plan
 IND#: 133692

FINAL Version 1.0
 2021-08-02

Pseudo code below will be used.

For comparing individual arms with placebo:

```
proc mixed data=imputed method=reml;
  class TRT01P(ref='Placebo') usubjid;
  by _imputation_;
  model &pftparm.=TRT01P BASE TRT01P*ady/noint solution ddfm=kr;
  random intercept ady/subject=usubjid type=un; *unstructured covariance
  structure had half of the trials not converge;
  estimate 'A_V_P' TRT01P*ady 1 0 0 -1/ CL;
  estimate 'B_V_P' TRT01P*ady 0 1 0 -1/ CL;
  estimate 'C_V_P' TRT01P*ady 0 0 1 -1/ CL;
  estimate 'T_V_P' TRT01P*ady 1 1 1 -3/ CL divisor=3;
  ods output Estimates=ran_coef_est(rename=(label=effect));
run;

proc mianalyze parms(classvar=full)=ran_coef_est;
  *class A_V_P B_V_P C_V_P A_V_B B_V_C A_V_C;
  modeleffects A_V_P B_V_P C_V_P A_V_B B_V_C A_V_C;
  ods output ParameterEstimates=rcrm_est;
run;
```

For combined active vs. placebo:

```
proc mixed data=imputed method=reml;
  class TRT01P(ref='Placebo') usubjid;
  by _imputation_;
  model &pftparm.=TRT01P BASE TRT01P*ady/noint solution ddfm=kr;
  random intercept ady/subject=usubjid type=un; *unstructured covariance
  structure had half of the trials not converge;
  estimate 'A_V_P' TRT01P*ady 1 0 0 -1/ CL;
  ods output Estimates=ran_coef_est(rename=(label=effect));
run;

proc mianalyze parms(classvar=full)=ran_coef_est;
  class A_V_P;
  modeleffects A_V_P;
  ods output ParameterEstimates=rcrm_est;
run;
```

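### SAP 11.1.1.2: the code for the exploratory lung-function slope model never pools the promised multiply imputed combined-active-versus-placebo contrast; a lesser point is that the non-convergence fallback in effect drops the random intercept

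*SAP*

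**What the plan says.** SAP 11.1.1.2 sets up a random coefficient regression for the key lung-function endpoints: "Table 2 lists key variables that will also be analyzed in RCRM". Table 2 marks six of them. The text promises that "Each individual/combined active arm will be compared with combined placebo arm" and that "This same analysis will be performed with and without multiple imputation".

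Two code blocks follow.

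- **First block (individual arms).** It estimates A_V_P, B_V_P and C_V_P, and also the combined contrast: "estimate 'T_V_P' TRT01P*ady 1 1 1 -3/ CL divisor=3". Its MIANALYZE step then pools "modeleffects A_V_P B_V_P C_V_P A_V_B B_V_C A_V_C".
- **Second block**, headed "For combined active vs. placebo". It fits the same model, estimates only "estimate 'A_V_P' TRT01P*ady 1 0 0 -1/ CL", names A_V_P in a CLASS statement and pools "modeleffects A_V_P".

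Time is in days, with random intercept and slope and an unstructured matrix. If that does not converge, the plan switches to compound symmetry, or removes the random intercept, or does both. SAP 7.3.3.5 presents the imputed lung-function runs as sensitivity analyses. SAP 10 and 11.1 call for lung-function results in both the mITT and EE Sets.

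**The concern.** The text and the code disagree about what is produced. A programmer who follows the code gets no multiply imputed combined slope from the first block. The second block's output carries the combined heading but is a different quantity. With 8 patients per dose, the combined comparison is the one most likely to be read, so a mislabelled version could mislead.

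The fallback raises a separate modelling question. Compound symmetry on an intercept and a per-day slope sets two variances with different units equal to each other. If that removes the random intercept in practice, lasting level differences between patients are loaded onto the slope, and the slope standard error is wrong.

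**Working it through.** The plan states no slope standard error or power, so there is no figure to reproduce.

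**1. Labels.**
- Estimated in block 1: A_V_P, B_V_P, C_V_P, T_V_P.
- Pooled in block 1: A_V_P, B_V_P, C_V_P, A_V_B, B_V_C, A_V_C.
- Estimated but not pooled: T_V_P. Pooled but not estimated: A_V_B, B_V_C, A_V_C.

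**2. What block 2 estimates.** Placebo is the reference level and is taken to come last, as block 1's coefficients imply.
- Four levels: 1 0 0 -1 is arm A minus placebo. With example slopes 0.01, 0.02, 0.03 and 0, T_V_P gives (0.01 + 0.02 + 0.03)/3 - 0 = 0.02; block 2 gives 0.01.
- Two levels: active gets 1, placebo gets 0, and the last two coefficients have no level to act on. With an active slope of 0.02 and placebo of -0.05, the difference is 0.07; the code returns 0.02 or no estimate. How the software treats surplus coefficients is an assumption, but neither outcome is a difference from placebo.

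**3. Size on the four-level reading.** Each cohort plans 8 active and 4 placebo patients (Protocol 4.1), so the arms are 8/8/8 and 12. Arm A versus placebo uses 8 + 12 = 20 of 36. With equal per-patient slope variance and complete data, the standard-error ratio is sqrt(1/8 + 1/12) / sqrt(1/24 + 1/12) = 0.456/0.354 = 1.29. Results affected: 6 endpoints x 2 sets = up to 12.

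**4. Why the fallback loses the intercept.** Under `type=cs` the intercept variance (points squared) must equal the slope variance ((points/day) squared). In a REML simulation of this design (30 runs per setting), true intercept SDs of 1 to 8 points were estimated at 0.03 to 0.07, and standard errors were within about 1% of a fit with no intercept.

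The result also depends on the time unit. With intercept SD 4, slope SD 6 points per 24 weeks, residual SD 3 and correlation 0, the large-sample ratio of model standard error to true SD under `type=cs` is 1.28 in days but 0.87 in 24-week units. Without an intercept it is 1.29 in both. This setting only illustrates unit dependence; its intercept SD lies outside the range in step 5.

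**5. Size of the distortion.** The documents give no variances. Assume linear trajectories and a baseline with the same residual error as later visits. Let b be the between-patient SD, s the slope SD per day, r their correlation and e the residual SD. Conditional on baseline, with q = b² + e²:
- intercept variance g11 = b²e²/q
- covariance g12 = r·b·s·e²/q
- slope variance g22 = s² - (r·b·s)²/q

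So the intercept SD cannot exceed the residual SD.

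For complete, balanced data and no random intercept, the large-sample fit gives

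ratio² = 1 + (k1·g11 + k2·g12) / (g22 + e²/Stt)

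where, with m visits, T = Σt² and a = (Σt)²/T:
- k2 = 2Σt/T
- w = (m - a)/(m - 1)
- k1 = (a - w)/T + w/Stt

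Spirometry, Days 29 to 169: Σt = 594, T = 72,526, Stt = 13,720, so k1 = 8.05×10⁻⁵ and k2 = 0.01638. DLco, Days 85, 141, 169: Σt = 395, T = 55,667, Stt = 3,658.7, so k1 = 7.55×10⁻⁵ and k2 = 0.01419.

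Range assumed: b 5-20, s 2-6 points per 24 weeks (divide by 168), r -0.8 to 0.3, e 1.5-3.
- **High end** (b 20, s 2, r 0.3, e 3): g11 = 8.80, g12 = 0.00157, g22 = 1.29×10⁻⁴. Spirometry: 1 + 7.34×10⁻⁴/7.85×10⁻⁴ = 1.935, ratio 1.39. DLco: 1 + 6.87×10⁻⁴/2.589×10⁻³ = 1.265, ratio 1.12.
- **Low end** (b 5, s 6, r -0.8, e 3): g11 = 6.62, g12 = -0.0378, g22 = 6.75×10⁻⁴. Spirometry: 1 - 8.7×10⁻⁵/1.331×10⁻³ = 0.935, ratio 0.97. DLco: 1 - 3.7×10⁻⁵/3.135×10⁻³ = 0.988, ratio 0.99.

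Under `type=cs` in days the ranges are nearly the same: 0.96-1.39 and 0.99-1.12. Median ratios without the intercept are about 1.20 and 1.08.

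**The case against.** The strongest reply is that the prose states the comparison correctly, T_V_P is coded correctly in the first block, and the listing is called pseudo code. Only imputed runs are touched, and these are sensitivity analyses of an exploratory model that supplements the MMRM, with no formal testing (SAP 7.4.1, 7.5). All of that stands and limits the importance of the point. It does not remove the error: the SAP says the code will be used, and the block carrying the combined heading does not estimate a combined difference on either reading. The 20 of 36 patients and the factor 1.29 apply only if four treatment levels are used there; for two levels no such factor can be given.

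On the fallback, a reader might infer a severalfold distortion. If intercept SD is allowed to run freely from 1 to 8 points against a residual SD of 1.5 to 3, the ratio under `type=cs` spans 0.76-4.37 for spirometry. The plan does not support that range. The model adjusts for baseline, and both schedules place lung function on Day 1, so under linear trajectories the remaining intercept SD is bounded by the residual SD.

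A reader might also take the code comment about half of the trials not converging to mean that half of these analyses will need the fallback. The comment is unexplained and does not say which trials it refers to, so how often a fallback is needed is unknown.

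**Conclusion.** The code error is certain from the text: as written, no step yields the multiply imputed combined slope contrast for any of up to 12 results. It would be wrong to infer that the model has no valid combined comparison, because the un-imputed T_V_P is correct. No primary conclusion is affected.

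The fallback is a real but lesser defect, and it arises only when the unstructured fit fails. Slope intervals would then usually be modestly too wide. Slight narrowing appears only with a strongly negative intercept-slope correlation. These sizes rest on assumed variances, balanced complete data and large-sample limits. They could be larger if the baseline measurement is older than Day 1 or if early change is non-linear, for example around the steroid taper on Days 15-50. Overall this is a minor correction to an exploratory analysis.

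**What to change.** **Code.**
- In the first MIANALYZE step, pool A_V_P, B_V_P, C_V_P and T_V_P, and delete A_V_B, B_V_C and A_V_C.
- Delete the second block. Alternatively, recode its contrast as 1 -1 on a two-level pooled factor, give it a label for the combined comparison, and remove its CLASS A_V_P statement.

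**Fallback.** Replace the sentence with a fixed order: rescale time and retry the unstructured fit; if that fails, use separate intercept and slope variances; if that fails, keep the random intercept only. Delete compound symmetry and the option to remove the intercept.

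The cost is a few lines of pseudo code and one sentence, with no effect on data or patients.

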11.1.2. Whole body 18F-FDG-PET/CT

SUV_{max} as measured by whole body ¹⁸F-FDG-PET/CT at screening and week 16/early termination visits. Patients with glucose levels above 11 mmol/L (200 mg/dL) have their scan delayed or be rescheduled as appropriate. Patients who did not have measures both at screening and at Week 16 (+/- 3 days) will not be included in change from baseline calculations, but will be included in by absolute value summaries. The measure may also be performed during an unscheduled visit within 3 days of the week 16 visit. If a patient has no

aTyr Pharma, Inc.
 Study ATYR1923-C-002 Statistical Analysis Plan
 IND#: 133692

FINAL Version 1.0
 2021-08-02

measures at Week 16/early termination visit, but has an unscheduled visit within 3 days of week 16/early termination visit, then the unscheduled visit will be used.

The three end points for PET scan will be as follows –

- Change from baseline in the highest SUVMax for an entire region - lung
- Change from baseline in the highest SUVMax for an entire region - lymph nodes
- Change from baseline in the highest SUVMax for an entire region - extra thoracic

Baseline SUV Max is the highest SUV max for all the focal lesions in a given region (e.g. lung). Post baseline SUV max is the highest SUV max for all the focal lesions in a given region (e.g. lung). It is noted that the baseline and post baseline highest SUV max may not be in the same focal lesion but will be in the same region.

Boxplots will also be created for SUV max by treatment by timepoint. Separate plots will be created for each region.

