- 6. **Pulmonary Function Testing** is to be performed using the same spirometer throughout the study. Parameters include forced vital capacity (FVC), forced expiratory volume in 1 second (FEV₁), FEV₁/FVC ratio at all specified visits. A minimum of 3 efforts should be obtained that meet the acceptance criteria of the American Thoracic Society or European Respiratory Society.
- 7. **DL**_{CO} measurements *should* be obtained after patients have been sitting quietly for 5 minutes.
- 8. Pregnancy serum tests are to be performed on all females at Screening and at Week 24/EOS. A urine pregnancy test is to be performed at other time points indicated.
- FSH only required for all female patients.
- 10. **Urinalysis** (semi-quantitative by dipstick): microscopy is to be performed if indicated by an abnormal and clinically significant result.
- 11. Serum Complement, Tryptase/Plasma Complement, and IgE are to be collected at Day 1 pre-dose and again if an infusion related reaction (IRR) occurs.
- 12. ¹⁸F-FDG-PET/CT scans are optional; patients who elect to participate agree to have imaging performed within 4 weeks prior to Day 1, and within ±5 days of Week 16 or if early termination prior to Week 16.
- 13. **Skin lesion evaluation:** To be completed for patients with skin lesions present. Skin lesions will be evaluated by: Skin Physician Global Assessment (SPGA), body surface Area assessment, the Sarcoidosis Activity and Severity Index (SASI).
- 14. **Skin lesion biopsy:** Optional for patients with skin lesions present. A non-target lesion (ie, a lesion that is not being assessed by SASI over time) is to be selected by the Investigator for biopsy during Screening and confirmed by the patient that it had been identified by his or her private dermatologist as cutaneous sarcoidosis. Skin lesion biopsy may be obtained within 4 weeks prior to Day 1 for patients who are otherwise deemed eligible for the study and within ±5 days of Week 12 or if early termination prior to Week 12.
- 15. **Randomization** is to be performed within 0-3 days prior to Day 1 or on the day of dosing.
- 16. **ATYR1923 serum PK** samples are to be collected pre-dose on dosing days. On Day 1 and Week 20 visits, PK samples are also collected post start of infusion at: 1 hr (just prior to [i.e., within 0-10 minutes] EOI), and at any single time point between 4-6 hours.
- 17. **ADA** samples are to be collected pre-dose when obtained on dosing days.

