6.4. Withdrawal and Replacement of Patients

6.4.1. **Study Drug Discontinuation Criteria**

Study drug must be discontinued if any of the following events occur:

- A serious adverse event (SAE) during or within 60 minutes of IV infusion that includes cardiac and/or respiratory observations, that has a reasonable possibility of a causal relationship with the study drug, including a severe IRR.
- Pregnancy.
- Patient request to discontinue study drug dosing for any reason.
- Other findings that, at the discretion of the Investigator and/or Sponsor, indicate that study drug administration should be discontinued.
- Missing 2 consecutive study drug doses.

The Investigator has full discretion to stop study drug infusion at any time, if clinically warranted or in the patient's best interest.

All patients who have been dosed with any amount of study drug will continue to be followed for safety. Patients who discontinue study drug dosing at any time during the treatment period should return to the study center for the EOS visit and as clinically indicated. Patients who have skin lesions that are being followed and withdraw from the study prior to Week 12 will be asked to have a skin biopsy at the EOS Visit. If applicable, patients who withdraw from the study prior to Week 16 will be asked to have a ¹⁸F-FDG-PET/CT at the EOS Visit.

Patients who decide not to receive any further study drug will be offered all follow-up safety assessments, including the EOS visit after their last infusion.

If a patient fails to attend scheduled study assessments, the Investigator must determine and document the reasons and the circumstances as completely and accurately as possible.

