8.4.6. Whole Body ¹⁸F-FDG-PET/CT

In this study, patients who elect to do so will undergo whole-body head to mid-thigh ¹⁸F-FDG imaging on a PET/CT scanner with a reconstructed resolution of ≤5 mm. Whole body ¹⁸F-FDG is to be performed within 4 weeks prior to Day 1, within ±5 days of Week 16, or at early termination if occurring prior to Week 16. Patients with glucose levels above 11 mmol/L (200 mg/dL) should have their scan delayed or be rescheduled as appropriate. The blood glucose level measured prior to the radiotracer administration should be recorded in an image transmittal form. Patients are to fast for a minimum of 4 hours prior to the injection of ¹⁸F-FDG. During the uptake phase, patients are to rest quietly and to refrain from talking, walking, and any other muscular activity to prevent non-specific FDG uptake in the skeletal muscles. The radiotracer will be administered through an IV line, after which the patient will be positioned comfortably in a supine position to rest for 60 to 90 minutes while the radiotracer distributes through the body.

Patients will be asked to void their bladder prior to the scanning procedure.

A whole body low-dose attenuation correction CT will be acquired with a whole body effective dose of 1.5 mSv. The maximum injected radioactivity dose of 555 MBq of ¹⁸F-FDG will result in a maximum whole body effective dose per PET/CT timepoint of ≤8.5 mSv, dependent upon patient habitus and calculated injected activity. As a weight-

based dose approach is allowed and is dependent upon subject weight, it is possible that in large or obese patients, a higher ¹⁸F-FDG activity may be required to ensure sufficient imaging quality; however in such cases, the injected activity will not exceed 555 MBq.

The baseline and follow-up ¹⁸F-FDG uptake PET scan will be assessed centrally by a qualified nuclear medicine physician visually and quantitatively using standardized uptake values (SUVs) and results will be compared with baseline scan. SUV is taken as an index of disease activity. Total injected activity and body weight will be recorded and used to compute SUV values. PET response will be determined by the nuclear medicine physician according to the European Organization for Research and Treatment of Cancer criteria.

The total dose for all PET scanning in this protocol will be maximally 17 mSv in larger or obese patients who have received a higher ¹⁸F-FDG injected dose.

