5. **12-lead ECG** is to be obtained at Screening, within 1-hour pre-dose on dosing days. At Day 1 and Weeks 12 and 20, an ECG is to be obtained at 4 hours (± 30 minutes) after SOI. The ECG is to be obtained after patients have been lying supine for 5 minutes.
6. **Pulmonary Function Testing** is to be performed using the same spirometer throughout the study. Parameters include forced vital capacity (FVC), forced expiratory volume in 1 second (FEV₁), FEV₁/FVC ratio at all specified visits. A minimum of 3 efforts should be obtained that meet the acceptance criteria of the American Thoracic Society or European Respiratory Society.
7. **DLco** measurements *should* be obtained after patients have been sitting quietly for 5 minutes.
8. **Pregnancy** serum tests are to be performed on all females at Screening and at Week 24/EOS. A urine pregnancy test is to be performed at other time points indicated.
9. **FSH** only required for all female patients.
10. **Urinalysis** (semi-quantitative by dipstick): microscopy is to be performed if indicated by an abnormal and clinically significant result.
11. **Serum Complement, Tryptase/Plasma Complement, and IgE** are to be collected at Day 1 pre-dose and again if an infusion related reaction (IRR) occurs.
12. **¹⁸F-FDG-PET/CT scans are optional**; patients who elect to participate agree to have imaging performed within 4 weeks prior to Day 1, and within ± 5 days of Week 16 or if early termination prior to Week 16.
13. **Skin lesion evaluation**: To be completed for patients with skin lesions present. Skin lesions will be evaluated by: Skin Physician Global Assessment (SPGA), body surface Area assessment, the Sarcoidosis Activity and Severity Index (SASI).
14. **Skin lesion biopsy**: Optional for patients with skin lesions present. A non-target lesion (ie, a lesion that is not being assessed by SASI over time) is to be selected by the Investigator for biopsy during Screening and confirmed by the patient that it had been identified by his or her private dermatologist as cutaneous sarcoidosis. Skin lesion biopsy may be obtained within 4 weeks prior to Day 1 for patients who are otherwise deemed eligible for the study and within ± 5 days of Week 12 or if early termination prior to Week 12.
15. **Randomization** is to be performed within 0-3 days prior to Day 1 or on the day of dosing.

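### SAP 11.1.2 admits PET scans to change from baseline only within 3 days of Week 16, where the protocol allows 5, and it is inconsistent on early-termination scans

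*SAP*

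**What the plan says.** **Protocol.** Section 8.4.6 places the follow-up scan "within ±5 days of Week 16, or at early termination if occurring prior to Week 16". Footnote 12 of Table 1 agrees: "within ±5 days of Week 16 or if early termination prior to Week 16". Section 6.4.1 adds that, where relevant, "patients who withdraw from the study prior to Week 16 will be asked to have a ¹⁸F-FDG-PET/CT at the EOS Visit".

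**SAP, schedule.** Section 5.1 reproduces the protocol's Table 1. Its footnote 12 has the same 5-day window and the same alternative, "or if early termination prior to Week 16".

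**SAP, analysis.** Section 11.1.2 makes five statements that bear on this point:

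- SUVmax is measured "at screening and week 16/early termination visits".
- Patients without scans "both at screening and at Week 16 (+/- 3 days) will not be included in change from baseline calculations".
- Patients left out under that rule are not dropped altogether, since the sentence ends "but will be included in by absolute value summaries".
- If there is no scan at that visit but the patient "has an unscheduled visit within 3 days of week 16/early termination visit, then the unscheduled visit will be used".
- The three PET endpoints (lung, lymph nodes, extra-thoracic) are each a change from baseline in the highest SUVmax of the region.

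**SAP, declared changes.** Section 3.3 covers the analysis sets, the time-adjusted steroid AUC and the steroid analysis periods. It does not mention PET.

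**The concern.** A site can scan a patient on a day that the protocol allows, and the analysis rule can then leave that patient out of every PET endpoint. No reason is given for the tighter window. It matches the general 3-day visit window in Table 1, which footnote 12 widens for PET, so it may be a carry-over. That explanation is an inference.

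The documents themselves foresee scans away from the target day. High glucose means a delayed or rescheduled scan (Protocol 8.4.6, SAP 11.1.2), and Protocol 6.3.1 accepts that COVID-19 may push visits outside their windows.

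Each lost pair of scans counts. A cohort has 8 active and 4 placebo patients, and only those who opt in are scanned. The change and absolute-value summaries would also describe different sets of patients.

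On early termination, two programmers could build different datasets from the same section. If patients who leave before Week 16 differ in outcome from those who stay, the choice could affect the comparison between arms.

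**Working it through.** There is no sample size or power figure to reproduce, since SAP 6 says none was calculated. The check is a day count and a comparison of text.

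**Inputs**
- Week 16 = 16 × 7 + 1 = Day 113, which matches Table 1 in both documents.
- Protocol half-width: 5 days (8.4.6; Table 1 footnote 12).
- SAP half-width for change from baseline: 3 days (11.1.2).
- Window of the Week 16 visit itself: 3 days either side (Table 1), so Days 110 to 116.

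**Both windows anchored at Day 113**
- Protocol: 113 − 5 = 108 to 113 + 5 = 118, which is 11 days.
- SAP: 113 − 3 = 110 to 113 + 3 = 116, which is 7 days.
- Compliant but excluded: Days 108, 109, 117 and 118. 11 − 7 = 4, and 4/11 = 36% of permitted days.

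**Sensitivity to the anchor.** The unscheduled-scan rule counts 3 days from the Week 16 visit, which could mean the actual visit on Day v.
- If only v − 3 to v + 3 counts, a visit on Day 115 keeps Days 112 to 118 and drops Days 108 to 111 (4 days). A visit on Day 110 keeps Days 107 to 113 and drops Days 114 to 118 (5 days). Over v = 110 to 116, 4 or 5 permitted days are dropped for a given patient.
- If a scan counts when it is within 3 days of Day 113 or within 3 days of the actual visit, v = 115 keeps Days 110 to 118 and drops only Days 108 and 109. Over v = 110 to 116, 2 to 4 permitted days are dropped.
- If both documents count from the actual visit, the result is again 11 − 7 = 4 days.

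Moving the anchor changes which days are lost. It does not remove the mismatch.

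**Early termination.** SAP 11.1.2 groups Week 16 with early termination when it states when SUVmax is measured, and again in the substitution rule for unscheduled scans. The one sentence that decides entry to change from baseline names Week 16 alone. With Day 113 as the anchor, an early-termination scan before Day 110 cannot satisfy that sentence. The substitution rule says which scan is used, but not that it enters change from baseline.

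**With the window set to 5 days.** Eligible days go from 110–116 to 108–118, and the four days are restored.

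**The case against.** The strongest reply is that little is lost. Excluded scans remain in the absolute-value summaries, and SAP 11.1.2 also plans boxplots of SUVmax by treatment and timepoint. PET is optional and exploratory, SAP 7.4.1 rules out formal hypothesis testing, and no PET model is specified. All of this stands, and it limits the weight of the point. It does not answer it, because the three named PET endpoints are all changes from baseline.

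Three stronger readings are tempting, and the documents do not support them.

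- **About a third of change values would be lost.** A reader might infer this from 4/11. It would need scans spread evenly over the 11 days. The documents give no scan timing, PET uptake or dropout. If every scan falls within 3 days of Day 113, the loss is zero.
- **All early-termination scans are discarded.** They are not discarded from the analysis as a whole, and their exclusion from change is only the literal reading of one sentence. The substitution rule suggests that the authors may have meant these scans to be usable, so loose drafting is a fair explanation.
- **Leaving them out is plainly biased.** Patients who need more corticosteroid are to stay on blinded study drug and be followed (Protocol 7.1.6.3), so worsening does not itself require exit, and two consecutive missed doses linked to COVID-19 can lead to withdrawal (Protocol 6.3.1). An early scan also reflects shorter exposure and may fall before or during the Day 15 to Day 50 taper. Keeping it out of a Week 16 change is defensible and fits SAP 11.1, which omits a patient from a visit whose value is missing.

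**Conclusion.** The window conflict is established. SAP 11.1.2 uses 3 days, where two places in the protocol and the SAP's own footnote use 5, and SAP 3.3 does not declare the difference. Followed literally with Day 113 as the anchor, the rule removes compliant scans on 4 of 11 permitted days from all three PET endpoints. This is a share of days and not of patients. The number of patients affected cannot be worked out from the documents and may be none.

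The early-termination point is an internal inconsistency. Exclusion from change follows from a literal reading, but the intention is unclear. Whether such scans should enter the main change summary is a matter of judgement, and the plan should state its choice.

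The correction is worth making because it is cheap and the scanned subset is small. It does not touch the primary safety endpoint.

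**What to change.** - In SAP 11.1.2, set the change-from-baseline window to 5 days either side of Week 16, name Day 113 as the anchor, and apply the same window and anchor to unscheduled scans.
- Reconcile the early-termination wording. One workable form keeps the Week 16 change summary as the main one and adds a summary that includes early-termination scans, flagged in the table and listing, because they reflect shorter exposure and possibly a different taper stage.
- If the 3-day window was deliberate, keep it, give the reason and list it in SAP 3.3.

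**Cost:** SAP wording, matching programming and one extra descriptive summary. No new data are needed. The rule should be settled before unblinding, the point by which SAP 3.1 says the plan is to be final.
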